13.1 Introduction

In STAREE the primary responsibility for the safety of individual participants will rest with the participant's usual general practitioner who is a co-investigator in the study. Additionally, an independent Data and Safety Monitoring Board (DSMB) will be appointed and will have primary responsibility for monitoring the study data for adverse trends and drug-related serious adverse events (SAEs). The responsibilities of the DSMB are outlined in the STAREE DSMB charter and DSMB plan.

13.2 Safety Monitoring

Several types of safety issues and SAEs may occur in STAREE participants. At each point of contact with participants, STAREE staff will specifically query participants for adverse events. Information on adverse events may also be reported to study staff between study visits by participants through contact with the trial centre by phone or email.

Participants will be encouraged to discuss any adverse events with their usual GP. GPs will be notified by STAREE staff of any abnormal test results and the STAREE medical officer will be available to discuss any issues with participants or their GPs.

13.2.2 Adverse events (AE)

The definition of an Adverse Event (AE) in the STAREE trial has been adapted from the National Institute of Aging definition. At the designated intervals for event collection, participants will be asked about specific events of interest as well as any new diseases or conditions. AEs will be obtained by self-report and some may require supporting documentation. AEs will be reported biannually to the Data Safety Monitoring Board (DSMB) by blinded treatment group.

AEs identified during monitoring will be classified by a trained medical officer or senior investigator as either serious or non-serious, and as potentially related or unrelated to study medication. If the AE is deemed related, therefore an adverse drug reaction (ADR or AR), further classification will occur regarding whether it is an expected or unexpected AR (see Appendix 5).

As the potential adverse effects of the active study drug in STAREE are well documented, AEs that are expected will not be considered as SAEs unless they meet the criteria for an SAE (section 11.2.3)

Source: AE definition adapted from the National Institute of Aging AE and SAE 2012 guidelines:

https://www.nia.nih.gov/sites/default/files/niaaeandsaeguidelinesfinal011012_0.doc

13.2.3 Serious adverse events (SAE)

Serious adverse events (SAEs) or Serious Adverse Drug Reactions (Serious ADRs) are defined as any unfavourable medical occurrence that:

- is fatal

- is life threatening ⁱ.
- requires in-patient-hospitalisation or prolongation of existing hospitalisation ⁱⁱ.
- causes persistent or significant disability/incapacity
- is a congenital anomaly /birth defect ⁱⁱⁱ.
- is a medically important event or reaction ^{iv}. or
- is an accidental or intentional overdose.

Source: National Statement on Ethical Conduct in Human Research 2007; National Health and Medical Research Council Safety Monitoring and Reporting in Clinical Trials involving Therapeutic Goods November 2016

i. Life Threatening SAE: An SAE is considered life threatening when it places the participant at immediate risk of death from the event as it occurred.

ii. Hospitalisation: A hospitalisation is to be considered an SAE only if it is an official admission (inpatient) with a duration of more than 24hr or a minimum of 2 calendar days where exact time of stay is unavailable.

iii. Not applicable, since STAREE participants are aged 70 years or over at study entry

iv. In the opinion of the responsible investigator (i.e. an event that is not immediately life threatening, does not result in death or hospitalisation, but which may jeopardise the participant or require intervention to prevent one of the other SAEs listed above)

13.2.4 Suspected Unexpected Serious Adverse Events (SUSARs)

A SUSAR is defined as a SAE that is:

- not a predefined cardiovascular endpoint (see section 5),
- is unexpected (taking into account drug labelling and the participant history),
- is causally associated with the study medication based on a determination by a medical officer of 'definite', 'probable' or 'possible' using the Naranjo scale.

All SUSARs will be adjudicated by a study medical officer to determine if the event is unexpected in terms of both medication labelling and the participant's history.

A non-endpoint event will be deemed to be a SUSAR if:

- Evidence exists to support the possible association of the event with either or both of the medications (i.e. either the project office or the investigator has assessed the event as possibly causally related to blinded study medication); and
- The event is unexpected in terms of the product labelling for either product; and
- The event is unexpected in terms of the subject's history; and
- The event is serious as defined in section 11.2.

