2.4.1 Myopathy

All statins have been reported to cause myopathy with the severity ranging from asymptomatic increases in creatinine kinase to muscle aches and weakness to fatal rhabdomyolysis.²⁶ The precise mechanisms are not well-understood. Of note, these myopathies are dose dependent and may occur even after therapy has been tolerated for up to 1 year.²⁷ The estimated incidence of statin myopathy in trials has ranged from 1.4 to 5% with the lowest rates reported for atorvastatin at low or high dosage.^{27,28} Older age, female gender and concomitant use of inhibitors of cytochrome P450 3A4 are recognised risk factors for the development of statin myopathy.²⁹ There may also be a higher risk of disability in older adults using statins due to age-related sarcopaenia.³⁰

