13.3 Safety reporting

In general, only AEs pre-specified to be of specific interest and those that are deemed to be serious will be reportable. AEs of interest are diabetes, myopathy (muscle symptoms) and liver impairment.

All SAEs will be reported from the study sites directly to the study medical officer within 24 hours of their notification to the clinical sites (study centres).

SAEs will be reviewed by the medical officer and adjudicated as related or unrelated to study medication, and as expected or unexpected serious adverse events.

All SAEs and SUSARS will be reported by the study centre to the ethics committees and DSMB according to the following schedule:

- Related and expected SAEs, will be reported to the Human Research and Ethics Committee (HREC)
- Related and unexpected SUSARs will be reported to the HREC within 72 hours and to the RACGP and TGA within 15 days and followed up with detailed reports when available
- Unrelated SAEs will be reported to the STAREE DSMB bi-annually

All SAEs and SUSARs will be reported to the DSMB in summary format by blinded treatment arm (A and B).

The data and safety monitoring reports will be prepared by an independent statistician.

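### Section 13.2.4 tests unexpectedness against the participant's history as well as the labelling, so a serious, unlabelled event already attributed to study medication can lose its 72-hour and 15-day reports

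*Protocol*

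**What the plan says.** Protocol section 13.2.4 sets the SUSAR rule in three steps.

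- **Definition.** The event must not be a predefined cardiovascular endpoint, must be one that "is unexpected (taking into account drug labelling and the participant history", and must be one that "is causally associated with the study medication based on a determination by a medical officer", with a Naranjo rating of at least possible.
- **Adjudication.** A study medical officer is to "determine if the event is unexpected in terms of both medication labelling and the participant's history".
- **Bullet list for non-endpoint events.** Four conditions are joined by 'and': possible association with the medication, unexpected on the labelling, unexpected on the subject's history, and serious. Labelling and history have separate bullets.

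Section 13.3 then sets the reporting schedule. For the top category: "Related and unexpected SUSARs will be reported to the HREC within 72 hours and to the RACGP and TGA within 15 days". For the category below it: "Related and expected SAEs, will be reported to the Human Research and Ethics Committee (HREC". That second line carries no time limit and names neither the TGA nor the RACGP. Section 13.3 also has every SAE reach the study medical officer within 24 hours of notification to the site, and has the DSMB receive all SAEs and SUSARs in summary by blinded arm.

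**The concern.** A history that explains an event is a reason to doubt that the drug caused it. That question belongs to the causality criterion, which 13.2.4 already has. Once the medical officer has rated the event as at least possibly due to study medication, the remaining question for expedited reporting is whether the reaction is already known for the product. The participant's past illness does not answer that: an unlabelled reaction stays unlabelled whoever has it.

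Because history is applied again after attribution, the only events it can remove from SUSAR status are ones the trial has itself linked to study medication. At stake is the speed and destination of reports on new, serious, drug-attributed reactions. Section 2.4 of the protocol says the burden of statin adverse effects in older people has not been well studied, so these are reports the trial has reason to want promptly.

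**Working it through.** No sample-size, power or alpha figure bears on this point, so there is no stated figure to reproduce. The check is to apply the 13.2.4 conditions and follow each outcome through the 13.3 schedule.

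**The rule.** For an event that is not a predefined cardiovascular endpoint:

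SUSAR = related AND serious AND unexpected on labelling AND unexpected on history.

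**The cases.** Fix related = yes and serious = yes, and vary the other two conditions.

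| Case | Unexpected on labelling | Unexpected on history | SUSAR? | Reports under 13.3 |
|---|---|---|---|---|
| (a) | yes | yes | yes | HREC in 72 hours; RACGP and TGA in 15 days |
| (b) | yes | no | no | at most the related-and-expected line: HREC, no time limit |
| (c) | no | either | no | related-and-expected line: HREC, no time limit |

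Cases (a) and (b) have the same seriousness, the same causality rating and the same absence from the labelling. They differ only in the participant's history, and that difference alone removes both dated reports. Case (b) ends up with the same reporting as case (c), a reaction already in the labelling.

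**Is the conjunction really required?** The definition alone might be read loosely, as one overall judgement that weighs labelling and history together. Two other passages in 13.2.4 close off that reading. The adjudication sentence uses the word 'both', and the bullet list gives history its own line joined to the rest by 'and'.

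**What survives in case (b).** Three routes remain: the 24-hour notice to the study medical officer, the untimed HREC report, and DSMB review. For the last, section 14.6.1 provides data every six months or as requested. What is lost is the 72-hour HREC deadline and the 15-day report to the RACGP and TGA.

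**The case against.** The strongest defence is that the rule is deliberate. The causality bar is low: a rating of possible suffices, and in the bullet list it may come from either the project office or the investigator. Participants are aged 70 or over and will have many background events. A history test could keep the expedited stream from filling with such events. The aim is reasonable, but the causality rating is the place to achieve it. If history accounts for the event, the medical officer can rate it unrelated.

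It can also be said that the bullet list states when an event will be a SUSAR, not that nothing else can be one, and that the definition only takes history into account. The adjudication sentence answers both arguments.

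Some objections stand, and they limit how far the point can be taken. A reader might infer any of the following, and the documents do not support them:

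- **That 13.2.2 contradicts 13.2.4.** Section 13.2.2 says only that "further classification will occur regarding whether it is an expected or unexpected AR (see Appendix 5". Appendix 5 is not available here and could itself refer to history, so no contradiction is shown.
- **That the loss falls on the participants most susceptible to statin harm.** The nearest support is section 2.4.1, which lists risk factors for statin myopathy. The protocol treats myopathy as a known statin effect, so it belongs to case (c) and the history test does not alter its reporting. The passage says nothing about who has unlabelled reactions.
- **That a given share of SUSARs is lost.** No document gives a frequency, and any percentage would be a guess.
- **That such events go unreported.** They lose the dated reports only. The RACGP committee is also among the ethics committees in section 14.1.2, and the lead-in to the 13.3 schedule refers to the ethics committees in general. The RACGP may therefore still be informed, without a deadline.

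**Conclusion.** The point holds as a defect in the SUSAR definition. On the protocol's own wording, a serious, unlabelled, non-endpoint event attributed at least possibly to study medication is not a SUSAR when the participant's history makes it unsurprising. It then has neither the 72-hour HREC report nor the 15-day RACGP and TGA report.

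Per affected event, the effect is the loss of both dated reports, with the untimed HREC report and the internal and DSMB routes remaining. How many events would be affected cannot be stated from the documents. The conclusion does not depend on that number.

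It rests on two assumptions: that the bullets in 13.2.4 are applied as the conjunction they are written as, and that Appendix 5 does not override them. Nothing in the available text suggests that it does. The point concerns safety reporting only and does not affect the efficacy analyses. It should be corrected.

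**What to change.** Amend section 13.2.4 in three places:

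1. In the definition, remove participant history from the expectedness criterion, leaving the drug labelling.
2. In the adjudication sentence, have the medical officer judge unexpectedness against the labelling only.
3. In the bullet list, delete the condition that the event be unexpected on the subject's history.

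Add a sentence saying that the participant's history may inform the causality rating and has no role in expectedness. Then check that Appendix 5 uses the same reference for expected and unexpected reactions. The schedule in 13.3 needs no change.

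The cost is protocol wording, a matching line on the medical officer's adjudication form, and probably a small number of additional expedited reports. No extra participants, visits or tests are needed.

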13.3 Safety reporting

In general, only AEs pre-specified to be of specific interest and those that are deemed to be serious will be reportable. AEs of interest are diabetes, myopathy (muscle symptoms) and liver impairment.

All SAEs will be reported from the study sites directly to the study medical officer within 24 hours of their notification to the clinical sites (study centres).

SAEs will be reviewed by the medical officer and adjudicated as related or unrelated to study medication, and as expected or unexpected serious adverse events.

All SAEs and SUSARS will be reported by the study centre to the ethics committees and DSMB according to the following schedule:

- Related and expected SAEs, will be reported to the Human Research and Ethics Committee (HREC)
- Related and unexpected SUSARs will be reported to the HREC within 72 hours and to the RACGP and TGA within 15 days and followed up with detailed reports when available
- Unrelated SAEs will be reported to the STAREE DSMB bi-annually

All SAEs and SUSARs will be reported to the DSMB in summary format by blinded treatment arm (A and B).

The data and safety monitoring reports will be prepared by an independent statistician.

13.4 Adverse Events of Interest

13.4.1 New diagnosis of diabetes

Diabetes as diagnosed on the basis of:

1) an annual HbA1c or fasting plasma glucose test using the WHO criteria (a HbA1c value of 6.5% or higher or a fasting plasma glucose of 7.0 mmol/L or higher, with confirmation by a second test within 4 weeks; or

2) community-based testing during usual clinical care (GP or other clinicians e.g. hospitalisation with a hyperglycaemic crisis or classic symptoms of hyperglycaemia and a random plasma glucose test of 11.1 mmol/L and/or commencement of glucose lowering medication for glucose control).

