5.2.3 Exclusion criteria

Potential participants who meet any of the following criteria will be excluded from the study:

- A history of clinical cardiovascular disease (defined as myocardial infarction, angina, coronary artery angioplasty and/or stenting, coronary artery bypass grafting surgery, heart failure, stroke, transient ischaemic attack (TIA), carotid stenosis, abdominal aortic aneurysm and peripheral vascular disease),
- Clinical diagnosis of dementia, treatment with medications for dementia (e.g. donepezil (Aricept), rivastigmine (Exelon) or Galantamine (Galantyl) or a 3MS score < 78 on screening.
- A history of diabetes or evidence of diabetes on pathology results (WHO diagnostic criteria whereby HbA1c $\geq 6.5\%$ / 48 mmol/mol or fasting glucose ≥ 7.0 mmol/L on two consecutive tests),
- Total cholesterol > 7.5 mmol/L,⁴⁹
- Moderate or severe chronic kidney disease (persistent proteinuria whereby urine albumin: creatinine ratio > 30 mg/mmol⁵⁰ and/or eGFR < 45 ml/min/1.73m² on two consecutive tests),⁴⁹
- Moderate or severe liver disease (persistent elevations of transaminases of more than 3 times the upper limit of the normal laboratory reference range),
- Serious inter-current illness likely to cause death within the next 5 years such as terminal cancer or obstructive airways disease,
- Current participation in another interventional clinical trial,
- Absolute contraindication to statin therapy,
- Current use of statin therapy or other lipid lowering therapy for primary prevention and unwilling to stop therapy,

- Current long term or permanent use of potent cytochrome P450 (CYP) 3A4 inhibitors as specified in Appendix 3.

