5.6.1 Screening call

Potential participants will phone the study centre after they have received an invitation to participate in the study. At this phone screening call, they will be screened for eligibility to be included in the study. Those who pass this first screening stage will then be invited to attend baseline visit 1.

Figure 3: Participant Timeline

[figure not shown]

Table 2: STAREE measurement and study activity schedule. A single X (with no superscripts) indicates that all specified measures carried out. The presence of a superscript indicates that the corresponding specific assessment is performed at that time point.

Measurement/ Activity	Screening	Baseline visits (BV)			Post-randomisation			
	Screening call	BV 1	GP visit	BV 2	1 month call	Annual visits (without cognitive testing)	Annual visits (with cognitive testing)	Close out visit
Type of visit	phone	clinic or phone	clinic or telehealth	clinic or phone	phone	clinic or phone	clinic or phone	clinic or phone
Month in trial (week)	0	0	0	0	(4)			
Review inclusion/ Exclusion criteria	X	X	X	X				
Obtain informed consent		X						
Dispense study medication (supply posted after annual study visit once compliance checked)		X (run-in med only)		Posted (after randomisation)				
Medication titration					X			
Assess medication compliance				X		X	X	X
Concomitant medications		X				X	X	X
Blood pressure & heart rate/rhythm ^a , height ^b , weight ^c , waist:hip ratio ^c		X ^{a,b,c}				X ^{a,c}	X ^{a,c}	X
Lifestyle profile & personal medical history ^d , family medical history ^e & IPAQ-E ^f , physical function		X ^{d,e}		X		X ^{d,f}	X ^d	X ^d
Routine Laboratory testing, GP referral to local pathology Bloods ^{**} : fasting glucose ¹ , fasting lipids (TC, HDL, LDL, triglyceride) ¹ , Hb ² , CK ² , creatinine ³ , (eGFR) ³ , ALT ³ , AST ³ , HbA1c ³ , Urine: ACR ³		X ^{1,2,3}				X ³	X ³	X ^{1,3}
Measurement/ Activity	Screening call	BV 1	GP visit	BV 2	Post-randomisation			

	Screening	Baseline visits (BV)			Post-randomisation			
	Screening call	BV 1	GP visit	BV 2	1 month call	Annual visits (without cognitive testing)	Annual visits (with cognitive testing)	Close out visit
Type of visit	phone	clinic or phone	clinic	clinic or phone	phone	clinic or phone	clinic or phone	
Month in trial (week)	0	0	0	0	(4)			
Quality of life SF-36				X		X	X	X
Assess cognitive function 3MS [±] (and CES-D 10 to exclude depression); CAM ¹		X					X	X

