5.7.4 Annual Follow up visit

Each year after randomisation, participants will participate in a study visit with a Field Officer. Visits may be conducted face-to-face or by phone. Annual measurements will include cognitive tests and disability assessments, lifestyle questionnaires as well as physical measures. The Quality of Life (SF-36), Life Ability and Annual medical history questionnaires will be provided in an online format or posted to participants who have agreed to this. For all other participants these surveys will be conducted at face-to-face visits. Pathology will be repeated (excluding lipids). Participants will be asked about their recent medical history and any concomitant medications they are taking. Additionally, participants will be asked about serious adverse events (SAEs) and potential study endpoints.

Following notification, clinical information relating to any SAE or endpoint will be sourced through: a) medical record review and b) hospital records and discharge summaries.

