7.3 STAREE Healthy Ageing Biobank

Up to 2000 STAREE participants located near STAREE study sites with facilities for processing and storage of biospecimens (Melbourne, Perth and Hobart) will be invited to provide a blood and urine sample for the STAREE Healthy Ageing Biobank. This study aims to create a collection of biospecimens which can be used in future research to identify new biomarkers that are linked with development of clinical outcomes such as stroke, myocardial infarction, cancer and dementia.

8. Contingency plans for participant wellbeing

Participants will be advised to seek care from their usual treating GP (or other health care providers) for any medical condition arising during the course of the study. Any test measurement result that is outside the normal range will trigger a notification to the participant's GP.

Treating GPs will be co-investigators and provided with information about the study to aid the participant's involvement in the study (wherever possible).

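### Route 1 of the new-diabetes definition needs a repeat test within 4 weeks that the annual schedule does not provide, so two consecutive diabetic annual values do not count under that route

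*Protocol*

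**What the plan says.** Section 13.4.1 of the protocol defines new diabetes by either of two routes.

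- **Route 1** starts from "an annual HbA1c or fasting plasma glucose test using the WHO criteria" (HbA1c 6.5% or higher, or fasting glucose 7.0 mmol/L or higher) and counts the case "with confirmation by a second test within 4 weeks".
- **Route 2** is "community-based testing during usual clinical care", with examples that include "commencement of glucose lowering medication for glucose control". It has no time window.

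The entry criterion in 5.2.3 uses the same thresholds and excludes people with HbA1c at that level or "fasting glucose ≥ 7.0 mmol/L on two consecutive tests". It gives no interval between the tests.

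The Table 2 row "Routine Laboratory testing, GP referral to local pathology" marks HbA1c at baseline visit 1, at annual visits and at close-out. It marks fasting glucose only at baseline visit 1 and close-out. No confirmatory test appears. Section 5.7.4 says of annual visits "Pathology will be repeated (excluding lipids", which suggests that fasting glucose is repeated yearly.

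The opening of Section 8 adds: "Any test measurement result that is outside the normal range will trigger a notification". The notice goes to the participant's GP. Section 13.3 lists diabetes as one of three adverse events of interest.

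**The concern.** A confirmation rule with a 4-week expiry sits on a test that the trial performs once a year. The schedule provides no second test inside the window, and the text does not say who arranges one. A participant with diabetic HbA1c at two successive annual visits would have been called diabetic at entry, yet does not qualify under route 1 during follow-up.

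The cases most exposed are mild ones: no symptoms, HbA1c just over the threshold, no treatment started. Annual testing is the means of finding these, and route 2 is least certain to pick them up.

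This matters because the protocol itself names diabetes as a statin harm. Section 2.4.2 cites a 9% increased risk, highest in trials of older participants, and 5.3.2 says the trial will inform the balance of benefit and harm in people over 70. A rule that lets confirmed cases drop out according to how quickly a GP retests makes the absolute harm estimate less dependable.

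**Working it through.** The protocol attaches no event rate, power or target count to new diabetes, so there is no figure to reproduce. The check sets the rules side by side.

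**1. Window against schedule.** Scheduled HbA1c tests are about 52 weeks apart and the window is 4 weeks: 52 / 4 = 13. The interval is about 13 times the window, so two scheduled annual tests cannot satisfy route 1. Reading 5.7.4 as making fasting glucose annual does not change this, because a yearly glucose test does not supply a repeat 4 weeks later either.

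**2. The same data under each rule.** Take HbA1c at or above 6.5% at two consecutive annual visits, with no other test.

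| Rule | Time limit | Counts as diabetes? |
|---|---|---|
| Entry, 5.2.3 | none | yes |
| Follow-up route 1, 13.4.1 | 4 weeks | no |
| Follow-up route 2, 13.4.1 | none | only if usual care diagnoses or treats |

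The wording of 5.2.3 leaves open whether the two-test condition covers HbA1c as well as glucose. On either reading, two consecutive high HbA1c values meet it. Liver impairment in 13.4.3, another event of interest, also requires two or more tests and sets no window.

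**3. When a participant is actually missed.** Both conditions must hold: (a) no repeat within 4 weeks of a positive annual test, and (b) no usual-care diagnosis or treatment under route 2. Each depends on action by the GP after notification. For community participants (5.4.3), the usual GP is not a co-investigator but does receive the results. A first positive at close-out has no later scheduled trial test.

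**4. Can the number be estimated?** No. Suppose the interval from first test to GP repeat is uniform (an assumption):

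- over 1 to 6 weeks, the share inside the window is (4 − 1) / (6 − 1) = 60%;
- over 2 to 12 weeks, it is (4 − 2) / (12 − 2) = 20%.

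Neither interval has a source in the protocol. Both calculations ignore route 2, which may well count the same late repeats. They show how sensitive route 1 is to retest timing and are not estimates of cases missed.

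**5. Effect of a given loss.** Let a fraction *c* of true cases be captured, equally in both arms. The absolute excess is multiplied by *c*. The standard error of the log hazard ratio is multiplied by about 1/√*c*, and the hazard ratio itself is roughly unchanged. For illustration only, *c* = 0.70 gives an absolute excess 30% too small and a standard error larger by 1/√0.70 = 1.20. The protocol supports no particular value of *c*.

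**The case against.** A reader might infer that a participant with two diabetic annual values is simply not counted. The documents do not support that. The two routes are alternatives, route 2 has no time limit, and its crisis, symptom and treatment items are introduced as examples. The GP is told of abnormal results, so two positive annual tests would prompt two notices. A GP repeat at week 5 can reasonably be read as usual-care testing and counted under route 2.

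A reader might also turn the retest arithmetic into a claim that 40% to 80% of test-detected cases are lost. That rests on assumed intervals and leaves out route 2.

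Further points for the plan:

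- A confirmatory test follows an abnormal result, so its absence from a visit schedule is not in itself an error. Table 2 lists no repeat for the entry rule either.
- An exclusion criterion and an event definition serve different purposes and need not match.
- HbA1c is collected every year, and fasting glucose/HbA1c is a tertiary endpoint (6.3), so glycaemic harm can be examined by arm in any case.
- The trial is double blind (5.7.3), so similar capture in the two arms is plausible.

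These points limit the size of the problem and remove any claim of certain loss or of bias in the hazard ratio. They do not remove the problem. Route 1 still discards confirmed results because of timing alone. The text does not say whether a late GP repeat is a failed route 1 or a valid route 2, so similar cases could be classified differently. Whether the mild, untreated case is counted still depends on the GP.

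**Conclusion.** The point holds in a limited form. Two consecutive annual values at the diabetes threshold do not count under route 1, while the entry criterion accepts two consecutive tests without a window. The participant is lost only when there is neither a repeat within 4 weeks nor a usual-care diagnosis or treatment.

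The number lost is unknown, because the protocol gives no diabetes rate, repeat-test rate or rate of GP action. If capture is similar across arms, the consequence is a lower absolute count and less precision for a pre-specified harm. Bias in the hazard ratio would need capture to differ by arm, and nothing in the document shows that it does. Neither co-primary endpoint nor the sample size is affected. The change is worth making because it is cheap and the HbA1c data are already collected.

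**What to change.** Reconcile 5.2.3, Table 2, 5.7.4 and 13.4.1 for event classification only. Diagnosis and clinical management are outside this change.

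1. In 13.4.1, count as new diabetes for analysis two consecutive results at the stated thresholds, from trial or community testing, even when the second falls outside 4 weeks. Date the event at the first positive test.
2. Keep the present 4-week version as a sensitivity definition, so that the effect of the window can be seen.
3. Settle whether fasting glucose is measured annually, as 5.7.4 and 13.4.1 suggest, or only at baseline visit 1 and close-out, as Table 2 shows.

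The cost is a few sentences and one extra tabulation. The HbA1c part needs no new data. The downside is a higher diabetes count in both arms and a slightly less strict case definition. A first positive at close-out would still need a community result to confirm it.
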